3 RESEARCH QUESTION/AIM(S)

How has the increased use of FFP3 style respirators during the COVID-19 Pandemic affected hospital doctor's facial hair?

Is there a difference between the prevalence of altered facial hair among those expected to perform aerosol generating procedures when compared to those who are not?

Are there doctors at RCHT who report religious or cultural reasons to changing their facial hair?

Have alternative forms of PPE been offered to those who do not achieve an adequate fit with FFP3 respirators?

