3.2 Outcome

To see if having facial hair in any context affected appropriate use of the FFP3. Consideration will also be given to if the current guidance is broad enough to offer an equal and diverse option of PPE FFP3 to all, in particular those with specific cultural, personal and ethnic needs and if not, what options can be taken to ensure that all staff needs are supported. Secondly, we will be looking to measure the personal impact on individuals having to remove facial hair because of the guidance and advice currently offering only one source of protection.

4 STUDY DESIGN and METHODS of DATA COLLECTION AND DATA ANALYSIS

The study design will be a cross sectional study in the form of a single survey.

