The population of interest are all hospital doctors at a Royal Cornwall hospital. A list of these doctors will be provided by the postgraduate centre, and an email, detailing the purpose of the research and an information sheet, will be circulated to these doctors, informing them that their participation is voluntary. In this email, there will be a link to a questionnaire which will take approximately 5 minutes to complete. The participants will not be required to input any identifiable information, so data will be anonymous to the researchers. Participants will be asked demographic questions such as age, gender, grade, department and whether they have the potential to be involved in aerosol generating procedures (AGP). They will also be asked if they passed fit testing, the most common level of PPE they wear at work, and whether they have been offered an alternative to a FFP3 mask. The participants will then be asked if they are able to grow facial hair, and if so they will be asked to select from a chart (taken with permission from Public Health England guidance) the styles which most resembled their facial hair before and after the first cases of COVID-19 were treated in our hospital. Participants will then be asked if their facial hair was influenced by FFP3 guidance, if they are happy with their current style, if they have any religious or culture reasons for maintaining their style, and whether there have been any religious, emotional or wellbeing effects to changing facial hair style. They will then be asked to select from a separate chart their favourite facial hair style, followed by any optional free text responses. The study will only be asking about FFP3 style respirator face protector PPE, and not any other form of protective equipment which may affect patient's hair.

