We have deliberately included all genders as not everybody identifies as either male or female, and the ability to grow facial hair is not limited to men. We have considered that we may offend female members of staff, however the email is generic to all doctors and not targeted to specific people. We also ask the question as such, "Do you grow facial hair which you can stylise? (This includes facial hair that you regularly shave, but does not include vellus or downy hair)". Our aim is to be as inclusive as possible, but to also not offend an already marginalised group of society (i.e. those who do not identify as either male or female). We suspect most of our responses will be from those identifying as male, but did not want to limit our population responses to this.

Data will be imported into Microsoft Excel, and statistical analysis will be performed using the R and R studio software packages. The odds ratio and relative risk will be calculated of a self-reported change in facial hair style in those who wore an FFP3 appropriate facial hair style prior to the COVID-19 pandemic versus those who did not, among the responders to the survey who reported they were able

to grow facial hair. Researchers will also calculate the odds ratio of a reported facial hair change in those expected to perform aerosol generating procedures versus those who were not. Confidence intervals will be calculated at the 95% confidence level. All statistical analysis will be performed by the researchers.

Once the study has ended and the final analysis of the project has concluded, the study documents will be archived for a minimum of 5 years in line with the Trust archiving Standard Operating Procedure RD&I SOP-07.

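### Research question 1 asks what FFP3 use did to facial hair, but the planned ratios count change for any reason and the item on FFP3 influence has no planned analysis

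*Protocol*

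**What the plan says.** Section 3 of the protocol opens with the main question: "How has the increased use of FFP3 style respirators during the COVID-19 Pandemic affected hospital doctor's facial hair". Its second question is narrower and names no cause: "Is there a difference between the prevalence of altered facial hair among those expected to perform aerosol generating procedures", compared with those not so expected. Section 3.2 adds that the study will "measure the personal impact on individuals having to remove facial hair because of the guidance".

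Section 4 describes two separate pieces of information. Respondents who can grow facial hair choose from a chart "the styles which most resembled their facial hair before and after the first cases of COVID-19 were treated in our hospital". This shows whether the style changed, but not why. Then comes an attribution item: "Participants will then be asked if their facial hair was influenced by FFP3 guidance".

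The analysis paragraphs of Section 4 name two comparisons. The first is introduced as "The odds ratio and relative risk will be calculated of a self-reported change in facial hair style" and is made "in those who wore an FFP3 appropriate facial hair style prior to the COVID-19 pandemic versus those who did not". The second is the "odds ratio of a reported facial hair change in those expected to perform aerosol generating procedures versus those who were not". Confidence intervals are at the 95% level. Neither outcome is limited to change attributed to FFP3, and the attribution item appears in no planned analysis.

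**The concern.** The main question is about cause, and the outcome in both comparisons is not. A doctor who grew a beard for reasons unrelated to masks counts as changed, exactly like one who shaved to pass a fit test. The survey is a single cross-section with no earlier period for comparison, so the background rate of style change is not measured directly.

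Comparing groups does not remove background change from a ratio. If it is similar in both groups, it pulls the odds ratio and relative risk towards 1. If it differs, it can move them either way and can produce an association where FFP3 had no effect. The survey collects an item that would give a more specific answer to research question 1, and the protocol does not put it to use.

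**Working it through.** **The plan's own figure.** Section 5.2.1 expects 20% of 1025 doctors: 1025 × 0.20 = 205, as stated. The point does not depend on this number.

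**Inputs.** The protocol gives no change rates, so all rates below are assumptions. Let *a* be the probability of FFP3-driven change in a group and *b* the probability of unrelated change, independent of *a*. Then

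P(any change) = 1 − (1 − a)(1 − b) = a + b − ab.

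**AGP comparison, equal unrelated change.** Take a = 0.40 (AGP) and 0.15 (no AGP), with b = 0.10 in both.

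- FFP3-driven change only: (0.40/0.60) / (0.15/0.85) = 3.78.
- Any change, AGP: 1 − 0.60 × 0.90 = 0.46. Any change, no AGP: 1 − 0.85 × 0.90 = 0.235.
- Odds ratio for any change: (0.46/0.54) / (0.235/0.765) = 2.77.

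**Range.** With a = 0.30 versus 0.10 and equal *b*:

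| b in both groups | Any change | Odds ratio | Relative risk |
|---|---|---|---|
| 0 | 30% v 10% | 3.86 | 3.00 |
| 5% | 33.5% v 14.5% | 2.97 | 2.31 |
| 10% | 37% v 19% | 2.50 | 1.95 |
| 20% | 44% v 28% | 2.02 | 1.57 |
| 30% | 51% v 37% | 1.77 | 1.38 |

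**Unequal unrelated change, no FFP3 effect.** With a = 0 in both groups and b = 0.20 versus 0.10, the odds ratio is (0.20/0.80) / (0.10/0.90) = 2.25 and the relative risk is 0.20/0.10 = 2.00. With the groups reversed, the odds ratio is 0.44. So the direction of distortion is not fixed.

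**Prior-style comparison.** Suppose FFP3-driven change is 5% in doctors already in an appropriate style and 50% in the others, with b = 0.10 in both. Any change is then 14.5% and 55%. In the protocol's order (appropriate style first), the relative risk moves from 0.05/0.50 = 0.10 to 0.145/0.55 = 0.26, and the odds ratio from 0.053 to 0.14. Of the changes in the appropriate-style group, (0.145 − 0.05)/0.145 = 66% would be unrelated to FFP3; in the other group, (0.55 − 0.50)/0.55 = 9%.

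**Limit on any remedy.** The appropriate-style group has little mask-related reason to change, so few of its members should report FFP3-driven change. If none do, the ratio in the protocol's order is 0, its inverse is undefined, and the usual log-based confidence interval does not exist.

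**The case against.** The other side has a good deal right.

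- **The AGP odds ratio answers its own question.** A reader might infer that both planned comparisons are the wrong analysis. Research question 2 asks only about altered facial hair, with no cause attached, so the AGP odds ratio fits it. The mismatch is with research question 1. This stands.
- **The prior-style comparison has a partial internal control.** Change among doctors already in an appropriate style gives some indication of ordinary change over the same period, so it is too strong to say that nothing is known about it. This stands, but the control is imperfect: background change may differ between the groups, and equal background change still alters a ratio.
- **Personal impact.** A reader might infer that doctors who changed for other reasons will be counted in the personal-impact result. Section 3.2 already defines that group as people removing hair because of the guidance, and nothing says the any-change group will be used instead. What is missing is only the item that identifies the group.
- **No inflated proportion is planned.** A reader might infer that the any-change proportion will be presented as the share affected by FFP3. The protocol plans ratios between groups and does not say this.
- **Tabulating a collected item is often left to a statistical analysis plan.** That is true, and an untabulated item alone would not be a finding. Here, however, the protocol itself names the outcome, groups, effect measures and confidence level, and fixes the outcome as any-cause change.
- **The item may not separate causes cleanly.** It asks whether guidance influenced facial hair, not whether it caused the change, and the questionnaire is not shown. Someone could answer yes for having kept a style. This is a reason to combine the item with an observed change and to show both versions.

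**Conclusion.** The point holds in a limited form. For research question 1, Section 4 analyses only undirected, any-cause change and leaves the FFP3-influence item without an analysis, so unrelated change enters both ratios. The planned comparisons are not invalid, and the AGP odds ratio should remain for research question 2.

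The size of the distortion cannot be computed from the protocol. The illustrated fall in the AGP odds ratio from 3.8 to 2.8 rests on assumed rates, on independence, and on equal unrelated change in the two groups. It would be wrong to conclude that the ratios are always pulled towards 1: the 2.25 obtained with no FFP3 effect shows the opposite when unrelated change is unequal. Nor should a ratio of attributed change by prior style become the sole answer to research question 1, because its appropriate-style cell may be close to empty.

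**What to change.** Keep both any-cause comparisons. Add to Section 4 a second outcome: the style changed and the respondent reports that FFP3 guidance influenced it.

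- For research question 1, report the proportion with this outcome and its 95% confidence interval, overall and separately by prior style (FFP3-appropriate or not). Do not rely on a ratio by prior style where the appropriate-style cell is near zero.
- Report the odds ratio of this outcome by AGP status beside the any-cause odds ratio.
- State that the same item identifies the group that Section 3.2 already defines for personal impact.

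The cost is a few lines of protocol text and a second run of similar calculations, with no new question or respondent. The downside is that attribution is self-reported and open to reporting bias, so both versions should be shown together.

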5.1.2 Exclusion criteria

The principle exclusion criteria are those who do not work at Royal Cornwall Hospital. Also, while not forming part of the exclusion criteria, those who are unable to grow facial hair will be excluded from the statistical analyses that involve reported odds and risks of change in facial hair.

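### The first planned odds ratio and relative risk need not equal 1 under no effect and do not give the shift in facial hair that the first research question asks about; a paired before/after estimate should be added

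*Protocol*

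**What the plan says.** The first research question in Section 3 is "How has the increased use of FFP3 style respirators during the COVID-19 Pandemic affected hospital doctor's facial hair".

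Section 4 plans two comparisons. For the first, "The odds ratio and relative risk will be calculated of a self-reported change in facial hair style", with the groups formed "in those who wore an FFP3 appropriate facial hair style prior to the COVID-19 pandemic versus those who did not". The second is an odds ratio of reported change by whether the doctor is expected to perform aerosol generating procedures, which matches the second research question. Of intervals, it says "Confidence intervals will be calculated at the 95% confidence level". Section 5.1.2 limits both comparisons to doctors who can grow facial hair.

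Section 4 also describes the data. Each respondent picks from a chart "the styles which most resembled their facial hair before and after the first cases of COVID-19 were treated in our hospital". There is an attribution item as well: "Participants will then be asked if their facial hair was influenced by FFP3 guidance". The analysis paragraph names no before/after estimate, gives change no direction, and does not say what value of the ratio would correspond to no effect.

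**The concern.** Apart from the aerosol-procedure comparison, the first contrast is the only analysis the protocol states, so it is the one left to answer the first research question. Its two groups are not doctors exposed and unexposed to FFP3 use. They are doctors who started on one side or the other of the line that the guidance draws. Growing a beard and shaving one off both count as change.

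Two things follow. First, ordinary turnover in styles can move the ratio away from 1, so a confidence interval that excludes 1 is not by itself a sign that FFP3 use changed anything. Second, the question concerns a shift among the doctors as a whole, and a ratio of two change rates does not fix that shift. A reader of the results could be misled about the study's title question even though the data to answer it more directly are collected.

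**Working it through.** **The plan's own figure.** Section 5.2.1 expects 1025 × 0.20 = 205 responders, which reproduces exactly. The protocol gives no baseline share, no change rates and no number able to grow facial hair. All of these are assumed below and varied.

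**Notation.** Of n responders able to grow facial hair, nA wore an appropriate style beforehand and nN did not; s = nA/n. Let b move from appropriate to not, and c from not to appropriate. In these examples change means crossing that line, with no moves within a class.

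- RR = (b/nA) / (c/nN)
- OR = [b/(nA − b)] / [c/(nN − c)]
- Paired shift = (c − b)/n, with standard error √[(b + c) − (c − b)²/n] / n

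Intervals are Wald, on the log scale for the ratios.

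**Check 1: zero net shift.** With b = c the paired shift is 0, and the RR reduces to nN/nA = (1 − s)/s. Take n = 205 and b = c = 16 (about 8% each way). The paired shift is 0.0 points (−5.4 to +5.4) in every row.

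| Appropriate beforehand | nA, nN | OR (95% CI) |
|---|---|---|
| 30% | 62, 143 | 2.76 (1.28 to 5.97) |
| 40% | 82, 123 | 1.62 (0.76 to 3.46) |
| 50% | 102, 103 | 1.01 (0.48 to 2.15) |
| 60% | 123, 82 | 0.62 (0.29 to 1.32) |
| 70% | 144, 61 | 0.35 (0.16 to 0.76) |
| 80% | 164, 41 | 0.17 (0.07 to 0.38) |

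For the first row, (16/46)/(16/127) = 127/46 = 2.76. With n = 100 and 8 moving each way, the odds ratios are nearly the same but less precise: 2.82 (0.94 to 8.42) at 30% and 0.17 (0.05 to 0.53) at 80%.

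**Check 2: one ratio, several shifts.** Fix the change rates at 10% (appropriate beforehand) and 40% (not), with n = 200. The OR is (0.10/0.90)/(0.40/0.60) = 0.167 and the RR is 0.25 whatever the baseline share. The paired shift is (c − b)/200:

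- 50% appropriate beforehand: (40 − 10)/200 = +15 points
- 60%: (32 − 12)/200 = +10 points
- 70%: (24 − 14)/200 = +5 points
- 80%: (16 − 16)/200 = 0
- 90%: (8 − 18)/200 = −5 points

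The size can also differ at a fixed baseline share. With 120 appropriate and 80 not, 6/120 v 40/80 gives RR 0.10 and a shift of +17.0 points (10.8 to 23.2). Equally, 3/120 v 20/80 gives RR 0.10 and +8.5 points (4.0 to 13.0).

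**Check 3: when the no-effect value is 1.** If guidance has no effect, the OR is the ratio of the background odds of change in the two groups. Rates of 5% v 15% give 0.30, 15% v 15% give 1.00, and 20% v 10% give 2.25. So 1 is possible but not guaranteed. Even when the OR is 1, the shift is not fixed. With 20% changing in both groups of n = 200, it is (28 − 12)/200 = +8 points at 30% appropriate beforehand and (12 − 28)/200 = −8 points at 70%.

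**The case against.** The contrast has a sensible rationale. Doctors already in an appropriate style had no guidance-driven reason to change, so their change rate is a rough guide to background turnover, and a higher rate among the others is indirect evidence that guidance mattered. The Background also frames the question as whether the guidelines are being followed, which suits a split on guideline-appropriate style. This stands, and it is why the contrast should be kept.

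A reader might infer that 1 can never be the no-effect value, or that the contrast is irrelevant to the first research question. The documents support neither. Check 3 shows that the value is 1 when background rates are equal, and the documents give no rates. Check 1 rests on one model of no effect, with equal counts crossing each way. The protocol's outcome is any change in style, so on its plain wording moves within a class count too, and these can shift the ratio either way. For example, 6 of 70 v 6 of 30 gives RR 0.43. Eight further within-class changes in the first group make it 14/70 v 6/30, RR 1.00, with the paired shift still 0. That argues against any particular figure. It also confirms that the ratio responds to things other than the shift.

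The paired shift has its own weakness: without a control group it includes any secular change. This stands too, so it should be added to the planned contrast and not be presented as proof of cause.

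Finally, an analysis plan that is not shown may contain a before/after table. But the protocol itself fixes the groups, outcome and measures of the contrast, and whatever is added elsewhere, that contrast alone would not answer the question.

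**Conclusion.** The point holds in a limited form. The no-effect value of the planned OR and RR need not be 1, and neither ratio gives the size or direction of the change in facial hair. Over assumed baseline shares of 30% to 80%, with 205 responders, zero net shift and only moves across the line, the OR runs from 2.76 to 0.17. Its interval excludes 1 at 30%, 70% and 80%, but not between 40% and 60%. Conversely, an OR of 0.167 fits shifts from +15 to −5 points. These figures illustrate and do not predict: the baseline share, the flows and the use of 205 as the analysed number are assumptions. The structural conclusion does not depend on them, because it follows from grouping on the starting level of the item that changes.

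**What to change.** In Section 4:

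- Keep the planned OR and RR as indirect evidence. Report the number and proportion changed in each baseline group beside them, and state that they are not to be read against 1 alone.
- For the first research question, add the 2×2 table of FFP3-appropriate style (yes/no) before by after, among responders able to grow facial hair. Report the change in proportion with a 95% CI for paired proportions, and McNemar's test if a test is wanted.
- Report this alongside the answers to the item on FFP3 influence, which bears most directly on attribution.

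The cost is one paragraph and one table; both chart items and the influence item are already in the questionnaire. The after margin of the table also gives the proportion in an appropriate style, which serves the adherence question in the Background. The downside should be stated in the protocol: the earlier style is recalled and there is no control group. A shift of 0 therefore means no net change over time, not proof of no FFP3 effect, and a non-zero shift may include other causes.

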5.2.1 Size of sample

A total of 1025 Doctors work at Royal Cornwall hospital, the questionnaire will be distributed to all Doctors. The sample will be the entire population of the hospital doctors at Royal Cornwall Hospital. We do acknowledge that there will be some drop out as people may not fill the questionnaire or fit the inclusion criteria, so at a 20% completion and inclusion rate, we suspect our sample will be around 205.

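### The aerosol-procedure comparison is planned as an odds ratio alone, although the question is about prevalence, and it makes no stated use of the pre-COVID style the survey collects

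*Protocol*

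**What the plan says.** Section 3 of the protocol poses the second research question in terms of prevalence: "Is there a difference between the prevalence of altered facial hair among those expected to perform aerosol generating procedures", compared with those who are not.

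Section 4 describes two comparisons of reported change among respondents able to grow facial hair:

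- By whether the style worn before the pandemic was FFP3-appropriate: "The odds ratio and relative risk will be calculated of a self-reported change in facial hair style in those who wore an FFP3 appropriate" style, against those who did not.
- By AGP status: "Researchers will also calculate the odds ratio of a reported facial hair change in those expected to perform aerosol generating procedures", against those who were not. Only the odds ratio is named here.

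Intervals are to be at the 95% level. Section 5.1.2 says that those unable to grow facial hair are "excluded from the statistical analyses that involve reported odds and risks of change in facial hair", so it speaks of risks as well as odds.

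Section 4 also says that participants choose from a chart "the styles which most resembled their facial hair before and after the first cases of COVID-19 were treated in our hospital". The stated analytic use of the earlier style is as the grouping variable in the first comparison. No stratification, adjustment or restriction by it is stated for the AGP comparison.

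Section 5.2.1 gives the expected size: "we suspect our sample will be around 205".

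**The concern.** There are two separate points.

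**Measure.** The question is on the prevalence scale and the planned measure is not. A single cross-sectional survey estimates both prevalences directly, so nothing in the design forces an odds ratio. Without the prevalences or their difference, a reader cannot tell how many more doctors in one group changed their facial hair.

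**Baseline style.** A doctor who already wore a suitable style has little FFP3-related reason to change it. The protocol recognises this by making earlier style the exposure in its first comparison. If the share with an unsuitable earlier style differs by AGP status, the crude odds ratio mixes that difference with any association between AGP duty and change.

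Both points bear on the stated purpose, in sections 1 and 2, of informing which protective equipment employers supply. Both can be answered from data the questionnaire already collects.

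**Working it through.** **The plan's own figure.** Section 5.2.1: 1025 × 0.20 = 205. It reproduces. The protocol gives no rate of change, AGP share or baseline-style share, so every rate below is an assumption chosen to show a range.

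**1. What an odds ratio leaves open.** For odds ratio OR and non-AGP prevalence p0, the AGP prevalence is p1 = OR·o0/(1 + OR·o0), with o0 = p0/(1 − p0). Take OR = (0.30/0.70)/(0.15/0.85) = 2.43.

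| Non-AGP p0 | AGP p1 | Difference | Relative risk |
|---|---|---|---|
| 5% | 11.3% | 6 points | 2.27 |
| 15% | 30.0% | 15 points | 2.00 |
| 40% | 61.8% | 22 points | 1.55 |

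**2. What baseline mix can do.** Let s be the share whose earlier style was not FFP3-appropriate, c the proportion of them who changed, and c0 the proportion who changed among the rest. The crude prevalence in a group is s·c + (1 − s)·c0.

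*AGP association within the unsuitable-style stratum* (c = 60% AGP, 30% non-AGP; stratum OR 3.5, relative risk 2.0):

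| s, AGP / non-AGP | Crude prevalences, c0 = 0 | OR | Crude prevalences, c0 = 5% | OR |
|---|---|---|---|---|
| 30% / 60% | 18.0% v 18.0% | 1.00 | 21.5% v 20.0% | 1.10 |
| 50% / 50% | 30.0% v 15.0% | 2.43 | 32.5% v 17.5% | 2.27 |
| 60% / 30% | 36.0% v 9.0% | 5.69 | 38.0% v 12.5% | 4.29 |

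In the 50/50 row with c0 = 0, the gap between 2.43 and 3.5 comes only from the odds-ratio scale: the relative risk is 2.0 both overall and in the stratum. The other rows show imbalance.

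*No AGP association within strata* (c = 45% in both groups):

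| s, AGP / non-AGP | Crude prevalences, c0 = 0 | OR | Crude prevalences, c0 = 5% | OR |
|---|---|---|---|---|
| 30% / 60% | 13.5% v 27.0% | 0.42 | 17.0% v 29.0% | 0.50 |
| 60% / 30% | 27.0% v 13.5% | 2.37 | 29.0% v 17.0% | 1.99 |

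A milder imbalance still moves the result. With 60% change in the unsuitable-style stratum and 5% in the other, in both AGP groups, shares of 40% / 60% give 27% v 38% and OR 0.60. The reverse gives OR 1.66.

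**3. Precision.** Wald 95% half-width for a difference: 1.96·√[p1(1 − p1)/n + p0(1 − p0)/n], with n per group. An equal AGP split is assumed, with half of each group in the unsuitable-style stratum.

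| Able to grow facial hair | Overall, 30% v 15% | Unsuitable-style stratum, 60% v 30% |
|---|---|---|
| All 205 (102.5 and 51.25 per group) | 15 ± 11.2: 4 to 26 points | 30 ± 18.4: 12 to 48 points |
| 103 (51.5 and 25.75 per group) | 15 ± 15.9: −1 to 31 points | 30 ± 25.9: 4 to 56 points |

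With all 205, the overall relative risk is 2.00 (1.16 to 3.46) and the odds ratio 2.43 (1.22 to 4.83).

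**The case against.** The strongest reply is that nothing is contradicted. The question asks whether prevalences differ; an odds ratio of 1 is the same as equal prevalences, and an interval is planned. Naming an odds ratio does not forbid group percentages, and the counts behind it would give them. Stratification is often left to an analysis plan, which may exist. The question is descriptive, so the crude comparison is its proper answer. The questionnaire also asks whether FFP3 guidance influenced the respondent's facial hair. And because the title speaks of increased FFP3 use, earlier style might itself partly reflect AGP duty, in which case adjusting for it would not clearly be better.

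Much of this stands. The odds ratio does answer whether there is a difference, and the crude comparison should remain the answer to the research question. The baseline point is the weaker of the two. It matters mainly if the AGP contrast is read as bearing on the main question of how FFP3 use affected facial hair. The possible link between AGP duty and earlier style is a reason to show strata beside the crude result, not to replace it.

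What does not stand is the defence of the measure. The protocol itself fixed the measures, and gave the relative risk to the adjacent comparison but not to the one whose research question is about prevalence. The attribution item records a respondent's stated reason; it does not show how many in each group began with a suitable style.

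**Conclusion.** The concern holds. The planned odds ratio is a valid test of whether the prevalences differ, but it does not give the size of the difference on the scale the question uses: under assumed rates, one value of 2.43 covers differences of 6 to 22 points. For the AGP comparison alone, no use of earlier style is stated. A twofold imbalance in that style could by itself produce a crude odds ratio of 0.42 or 2.37, or hide a stratum odds ratio of 3.5 behind a crude value of 1.00.

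These are illustrations. The documents do not indicate that such an imbalance exists, and its size and direction cannot be known before the survey. Confidence is therefore medium, and the change is one that should be made because it is cheap, not because the planned result would be invalid.

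**What to change.** In section 4 of the protocol:

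- Keep the comparison in all respondents able to grow facial hair as the answer to the second research question.
- State that the prevalence of reported change will be given for each AGP group, with the prevalence difference, the relative risk and the odds ratio, each with a 95% interval.
- Add a supplementary AGP comparison of the same outcome, stratified by whether the style before COVID-19 was FFP3-appropriate. Show each stratum beside a Mantel-Haenszel or baseline-adjusted summary. If nobody in one stratum changed, its odds ratio is undefined and the Mantel-Haenszel odds ratio rests on the other stratum alone; the prevalences and their difference can still be shown.

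The cost is one or two sentences and a few lines of R, with no new question, data or sample size. The drawback is precision: under the assumptions above, intervals widen from about ±11 to ±18 points if all 205 can grow facial hair, and from about ±16 to ±26 points if only 103 can. The stratified result should be labelled supplementary and read as such.
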